#### **6.4.6 Bleeding Events**

Clinically relevant bleeding is the main potential risk based on the pharmacological action of ALX-0081. Clinically relevant bleeding is assessed daily during daily PE period, on the first day after the daily PE period and then weekly for the subsequent time interval until 30 days after the last PE session and during any unscheduled visits. The number of subjects who experience clinically relevant bleeding and the number of subjects requiring surgical and/or medical intervention will be tabulated by treatment group and summarised by visit using counts and percentages.

Bleeding according to the modified ITP bleeding score is assessed daily during daily PE period, on the first day after the daily PE period and then weekly for the subsequent time interval until 30 days after the last PE session and during any unscheduled visits. Modified ITP bleeding score will be summarised for each parameter by treatment group and visit using counts and percentages. The sum of the parameter scores for each subject at each time point will be summarised using descriptive statistics for continuous variables.

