4.3 Overview of Treatment and Dosing Regimen for Study Drug

The primary treatment for acquired TTP is daily PE. Immunosuppressive treatment is also often administered. The centres will follow their respective guidelines for the treatment of TTP patients, regarding all items other than the study drug. Discontinuation of daily PE depends on normalisation of platelet count, neurological status and other clinical and laboratory parameters. The frequency of PE is occasionally reduced ('tapered') rather than stopping completely at time of response, however this is not based on randomised clinical trial data and is not recommended per this protocol (although it is allowed if considered necessary by the Investigator).

The study drug will be administered as adjunctive treatment at specific times relative to the PE procedures.

The first administration is a single i.v. bolus injection, administered by a push injection. All subsequent administrations are s.c. injections. The study drug consists of 10 mg of ALX-0081 or placebo, once daily (except if PE is given twice daily, then study drug is 10 mg twice daily) as described in Section 7.2.

Note that, in case of re-initiation of daily plasma exchange due to exacerbation, no i.v. bolus injection will be administered prior to the first new PE session; daily s.c. study drug administration will continue per protocol.

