- The neurocognitive battery, if NOT performed at baseline, will be administered once as soon as possible, i.e., when level of consciousness and attentiveness of the subject permits and environmental factors are appropriate to support neurocognitive testing (e.g., subject is able to sit upright and interact with computer touch screen; subjects have eyeglasses used for reading and hearing devices, if applicable; testing area is quiet and relatively free of distracting stimuli).
- The bleeding score according to the modified ITP bleeding score will be performed daily during daily PE period, on the first day after the daily PE period and then weekly for the subsequent time interval until the last day of study drug administration.
- Assessment of clinically relevant bleeding will be performed daily during daily PE period, on the first day after the daily PE period and then weekly for the subsequent time interval until the last day of study drug administration.
- 12-lead ECG daily during the hospitalisation if it was abnormal at baseline. In addition, an ECG will be taken on day 1 and day 4, 4-6 hours post-study drug even when ECG was normal at baseline. The ECG will also be performed at pre-discharge and weekly after discharge until the last day of study drug administration.

Sampling for local laboratory:

- Blood sampling for chemistry will include the following: glucose, AST, ALT, LDH, CRP, creatinine, urea (BUN), uric acid, protein, albumin, haptoglobin, Na, K, Ca, Mg and Cl (local laboratory). The blood sample will be drawn daily during daily PE period, on the first day after the daily PE period and then weekly until the last day of study drug administration.
- Blood sampling for haematology will include the following: haemoglobin, haematocrit, MCV, MCH, MCHC, full blood count including RBC, WBC, differential, reticulocytes, optical platelet count and immature platelet fraction (local laboratory). In case optical platelet counts are not available, they can be replaced by measurements based upon impedance. If not available in the local laboratory, immature platelet fraction measurements can be omitted; The blood sample will be drawn daily during daily PE period, on the first day after the daily PE period and then weekly until the last day of study drug administration.

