### 1.3 Study Timepoints

The subjects will be followed in 3 different phases during this study:

- Screening ( $\leq 12$  hours prior to first PE on study and study drug) and baseline (15 minutes-6 hours prior to first PE on study and study drug)
- Treatment Phase:
  - Daily PE adjunctive s.c. treatment phase
  - Day 1 after the last daily PE
  - Post daily PE s.c. treatment phase (including PE tapering)
- Follow-up Phase (after completion of study drug treatment):
  - Day 3 (+/- 1 day)
  - Day 7 (+/- 1 day)
  - Month 1 (+/- 3 days)
  - Month 2 (+/- 7 days)
  - Month 3 (+/- 15 days)
  - Month 6 (+/- 15 days)
  - Month 12 (+/- 15 days)

Subjects enrolled into the study under earlier versions of the protocol will also be followed up at Days 1, 2, 4, 5 and 6 of the Follow-Up Phase. Data for these time points will be included in summary tables and listings only for those subjects where the data was collected. Due to the lack of meaningful interpretation of a percentage based on the number of subjects in the population, the percentage for these time points will not be presented.

[Figure 1](#) displays a schematic overview of the different study phases and [Appendix I](#) contains the general schedule of assessments for this study.

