## 6.1 Statistical and Analytical Issues

### 6.1.1 Statistical Methods

All data will be summarised by treatment group. In addition, where appropriate, a total overall group column will be included to summarise all subjects. Where appropriate, data will be summarised by treatment group and visit or whenever the assessment is done (e.g. the 1 and 3 week post-last day PE sampling may be done at the weekly visit, even if not at exactly 1 or 3 weeks).

All data will be listed and some selected variables will be tabulated or presented graphically, and will be noted where appropriate.

In summary and analysis tables of continuous variables, the minimum and maximum statistics will be presented to the same number of decimal places as the original data. The mean, median, quartiles, Least Squares mean (LS mean), and 95% Confidence Interval (CI) will be presented to one more decimal place than the original data, the standard deviation (SD) and standard error (SE) will be presented to two more decimal places than the original data. Standard descriptive statistics (number of subjects with data available [n], mean, SD, median, minimum and maximum) will be presented in summary tables. The LS mean, SE and 95% CI will be presented in the statistical analysis outputs as appropriate.

In summary tables of categorical variables, the number of non-missing observations and percentages will be presented. The denominator for each percentage will be the number of subjects within the population of interest [N] (unless otherwise specified).

All hypothesis testing will be 2-sided unless otherwise specified and carried out at the 5% significance level and designed to evaluate the superiority of ALX-0081 to placebo.

P-values will be rounded to three decimal places. P-values less than 0.001 will be reported as <0.001. P-values greater than 0.999 will be reported as >0.999.

Should any of the statistical methods (other than the primary endpoint analysis) proposed prove unsuitable during the final analysis, more appropriate methods will be used, and any changes documented in the CSR, including the rationale for use.

All statistical analysis will be performed using SAS® v9.2 or higher.

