## 6.4 Safety Analysis

Analysis of all safety data will be performed on the safety analysis population.

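### By-visit bleeding percentages are taken over the whole safety population although only subjects still on daily PE are assessed daily, so the arm that stops PE sooner is diluted more

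*SAP*

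**What the plan says.** - **Display.** SAP 6.4.6 on the ITP items: "Modified ITP bleeding score will be summarised for each parameter by treatment group and visit using counts and percentages". On clinically relevant bleeding, it says the numbers of subjects "will be tabulated by treatment group and summarised by visit using counts and percentages".
- **Denominator.** SAP 6.1.1: "The denominator for each percentage will be the number of subjects within the population of interest [N] (unless otherwise specified". Section 6.4.6 specifies nothing different. SAP 6.4 fixes the population: "Analysis of all safety data will be performed on the safety analysis population".
- **Schedule.** SAP 6.4.6: "Bleeding according to the modified ITP bleeding score is assessed daily during daily PE period, on the first day after the daily PE period", and weekly after that. Protocol 8.1.2 agrees: "The bleeding score according to the modified ITP bleeding score will be performed daily during daily PE period". Clinically relevant bleeding follows the same schedule.
- **What ends daily PE.** Protocol 4.3: "Discontinuation of daily PE depends on normalisation of platelet count, neurological status and other clinical and laboratory parameters".
- **A precedent in the SAP.** SAP 1.3 drops percentages for follow-up days 1, 2, 4, 5 and 6, which only subjects under earlier protocol versions attended. Its reason begins "Due to the lack of meaningful interpretation of a percentage based on the number of subjects in the population". No such exception covers the daily-PE visits.

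**The concern.** The number assessed on a given day of daily PE falls as subjects stop PE, but the denominator stays at N. Stopping PE depends largely on platelet recovery, which is the platelet part of the primary endpoint, and the trial is sized on ALX-0081 reaching it sooner. A displayed percentage therefore mixes two things: how often assessed subjects bleed, and how many subjects are still being assessed. The second is expected to differ by arm, in the direction that flatters ALX-0081.

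SAP 6.4.6 names clinically relevant bleeding as the chief risk expected from the drug's pharmacology. Protocol 10.3 plans no formal testing of safety data, so readers will compare the arms from the descriptive tables. Protocol 8.3.3 adopted the modified ITP score because it was expected to be more sensitive than other bleeding scales, and SAP 6.4.6 plans no summary of its individual items other than the by-visit one.

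**Working it through.** **Inputs from the documents.** Median time to response is 6 days on control and 3.36 days on ALX-0081; power is 80%, one-sided 2.5%, 1:1 allocation, with 15% lost to follow-up and N = 110 (Protocol 10.4, SAP 6.1.4).

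**Check of the planning figures.** The hazard ratio is 6/3.36 = 1.786. Schoenfeld events = 4 × (1.960 + 0.842)² / (ln 1.786)² = 93.4, and 93.4/0.85 = 109.9, which matches the stated 110. The medians are therefore the ones the trial was sized on.

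**Assumptions not in the documents.**
1. Time on daily PE is exponential, ending either at response or two days later.
2. Bleeding prevalence p among assessed subjects is equal in both arms. It cancels from the ratio; 20% is used only for illustration.
3. There are 55 dosed subjects per arm.
4. The table has one row per day of daily PE. The table shells are not in the documents. SAP 6.1.1 speaks of summaries by visit or whenever the assessment is done.

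**Formulas.** Share still on daily PE at day d: S(d) = 0.5^(d/median), or 0.5^((d − 2)/median) with the two-day lag. Displayed percentage = p × S(d). Ratio ALX-0081/placebo = S_ALX(d)/S_placebo(d).

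| Day | PE ends at response: placebo, ALX-0081 | Ratio | PE ends 2 days later: placebo, ALX-0081 | Ratio |
|---|---|---|---|---|
| 3 | 0.707, 0.539 | 0.76 | 0.891, 0.814 | 0.91 |
| 5 | 0.561, 0.356 | 0.64 | 0.707, 0.539 | 0.76 |
| 7 | 0.445, 0.236 | 0.53 | 0.561, 0.356 | 0.64 |
| 10 | 0.315, 0.127 | 0.40 | 0.397, 0.192 | 0.48 |

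**Illustration at p = 20%, PE ending at response.** The table would read, placebo versus ALX-0081: 11.2% versus 7.1% at day 5, 8.9% versus 4.7% at day 7, and 6.3% versus 2.5% at day 10. With the number assessed as denominator, every row reads 20% versus 20%.

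**Break-even.** The reciprocal of the ratio is the true relative prevalence on ALX-0081 at which the two displayed percentages become equal. It is 1.57, 1.89 and 2.48 at days 5, 7 and 10, or 1.31, 1.57 and 2.07 with the lag.

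**Numbers assessed.** Of 55 per arm with PE ending at response, placebo versus ALX-0081: 30.9 versus 19.6 at day 5, 24.5 versus 13.0 at day 7, and 17.3 versus 7.0 at day 10.

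**The case against.** The strongest reply is that nothing is hidden. SAP 6.1.1 has the number of non-missing observations printed with the percentages, so the proportion among assessed subjects can be recovered. Grade 0 is a scored category of the ITP scale (Protocol 8.3.3), so a reader who infers that unassessed subjects are counted as free of bleeding would be wrong: grade 0 is diluted too, and the grades visibly fail to reach 100%. This stands. It limits the harm but does not make the percentage a sensible one to print.

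Second, other bleeding summaries do not share the fault. Clinically relevant bleeding is also tabulated by treatment group, and the summed ITP score is described on available data. Bleeding that meets the AE definition enters the per-subject tables of SAP 6.4.1, and after discharge the person giving study drug records bleeding daily (Protocol Table 11). This also stands. A reader might infer that the safety analysis as a whole will understate bleeding on ALX-0081; the documents do not support that.

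Third, the size depends on when PE stops. Protocol 4.3 lists neurological status and other parameters besides platelets, and response needs confirmation at 48 hours, hence the range above. If the day-after-PE and weekly assessments fall into the same study-day rows, dilution is weaker; if they are separate visits, they are little affected. All of it requires ALX-0081 actually to shorten PE.

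Fourth, it is tempting to extend the point to every by-visit safety table. Physical examination has its own category for examinations not done (SAP 6.4.2), and daily ECGs depend on an abnormal baseline ECG and hospitalisation (SAP 6.4.4), so the extension is weak there. It does fit by-visit abnormal laboratory results (SAP 6.4.5), because chemistry and haematology are drawn daily only during daily PE.

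Finally, no simple replacement gives a clean arm comparison. Subjects still on PE are slow responders, selected after randomisation. Worst grade per subject and bleeding days per assessed day both depend on how often subjects are assessed, which differs by arm. So neither should be made the required comparison.

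**Conclusion.** The point holds for by-visit percentages at daily-PE visits. As written, SAP 6.1.1 and 6.4.6 together produce percentages that fall with the number still assessed, and fall faster in the arm that leaves daily PE sooner. At equal bleeding among assessed subjects, and with the planning medians, the ALX-0081 figure would be about 24% to 36% below placebo's at day 5, 36% to 47% below at day 7 and 52% to 60% below at day 10.

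This is a downward bias at equal risk, not a forecast of what the table will show. A large enough true excess on ALX-0081 would still appear, and without a shortening of PE there would be no differential dilution. The practical consequence is greatest for the individual ITP items, which have no other planned summary. The reasoning in SAP 1.3 already rejects this kind of percentage for visits that only some subjects attend.

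**What to change.** Before database lock:

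1. In SAP 6.4.6, for clinically relevant bleeding and each ITP item by visit, specify the denominator as the number of subjects assessed at that visit and print it in each row.
2. Make the same change for by-visit abnormal laboratory results in SAP 6.4.5.
3. Add, as a supplementary row, each subject's worst post-baseline ITP grade over the treatment period, with N as denominator and a footnote that assessment frequency differs by arm.
4. Footnote the by-visit table to say that late daily-PE visits rest on small, selected groups of slower responders. On the assumptions above, about 17 placebo and 7 ALX-0081 subjects would remain at day 10.

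The cost is SAP wording and table programming; no new data are needed. The price is less stable percentages at late visits, which the printed n makes plain.

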#### **6.4.7 Immunogenicity**

ADA in serum will be determined by an immuno assay and processed at GLP Pharma. Immunogenicity testing will be performed on the timepoints indicated in [Appendix I](#). A separate immunogenicity report will be prepared and presented as an Appendix to the Final Clinical Study Report.

The number and percentage of subjects who developed anti-drug antibodies (ADA)  $\leq$  30 days post-last study drug treatment will be presented by treatment group and overall.

The number and percentage of subjects who developed ADA  $>$  30 days post-last study drug treatment will be presented by treatment group and overall.

#### **6.4.8 Glasgow Coma Score**

The Glasgow Coma Score will be determined using the Glasgow Coma Scale (original scale), which is a neurological scale that measures the conscious state of the subject. The best eye opening, verbal and motor responses will be scored according to the scale, and the separate scores added up to obtain the final score, ranging from 3 to 15. Scores will be summarised within each system (eye opening, verbal and motor) and final score by treatment group and visit for the Safety population.

### **6.5 PK/PD Analysis**

#### **6.5.1 Pharmacokinetics**

The plasma concentration-time profiles and summary statistics per treatment and overall will be presented for the PK population. Summary statistics will include: arithmetic mean, SD, coefficient of variation (CV) of the arithmetic mean, geometric mean, CV of the geometric mean, median, minimum and maximum.

A non-linear mixed effects pharmacokinetic/pharmacodynamic model will be used to describe the observed data. A separate Data Analysis Plan will describe the main objectives, steps and rules of the analysis. The results are outside the scope of this SAP and will be performed by the PK modelling group within Ablynx. The results will be reported in a separate study report.

#### **6.5.2 Pharmacodynamics**

The following assessments were taken at baseline and throughout the treatment phase for the pharmacodynamic (PD) analysis:

- RICO (conducted at central lab), presented as the number of subjects and days with RICO  $<$  and  $\geq$  20% during study drug treatment and in one month follow-up.
- vWF, including vWF:Ag and vWF propeptide (conducted at central lab)
- FVIII chromogene (conducted at central lab)
- Platelet count

---

Of the above, tables will be made using the safety population. Subject profile plots and summary statistics by parameter and treatment will be presented for the Safety population.

## **6.6 Interim Analysis**

An interim analysis for safety with formal stopping rules will be done when 28 of the ALX-0081 treated subjects have been treated and assessed. Upon review of the interim safety analysis, DSMB will then make a recommendation on study continuation or discontinuation.

Since no efficacy analyses will be conducted at the interim, no alpha adjustment is made. This DSMB review is covered separately in a DSMB SAP and Charter.

The formal statistical analysis is conducted once all data for the one month follow-up is clean and locked. There will be a second formal analysis at the end of the study, when the outputs including data up to the one year follow-up will be delivered.

## **6.7 Data Monitoring Committee Charter**

An independent DSMB monitors accruing safety data during the study (SAEs on an ongoing basis and 'early safety look' when 16 subjects, 8 ALX-0081 treated and 8 placebo treated, have completed treatment with study drug) and makes recommendations on continuation of the study. After recruitment of 56 subjects a formal safety review of the data is foreseen using a safety stopping rule. More details on this review and safety stopping rule can be found in the DSMB charter and SAP. No review of efficacy data by the DSMB is foreseen.

The members of the DSMB will be experts who are independent from the sponsor and the contract research organization (CRO). The procedures and responsibilities for the collection, analysis, and review of the data by the DSMB as well as communication and documentation of their opinions and recommendations are defined in the DSMB charter.

DSMB reviews are handled by IDDI, with no involvement from inVentiv Health Clinical Biostatistics.

## 7. TABLES, LISTINGS, AND FIGURES

The default tables, listings and figures (TLF) layout will be as follows.

Orientation	Landscape
Paper Size	A4
Margins	Top: 3.2 cm Bottom: 2.5 cm Left: 2.5 cm Right: 2.5 cm
Font	Courier New 9pt
Headers (Centre)	Sponsor name and Protocol number(Left); Page X of Y (Right) TLF Number and Title
Footers (Left)	SAS program path and file name Date TLF generated

The font size may be reduced as necessary to allow additional columns to be presented, but not at the expense of clarity. Also the orientation may be changed to portrait if appropriate.

The date format for all presentations will be 'DDMMYYYY'.

All TLF outputs will be generated using SAS® v9.2 or higher for Windows.

CRF data collected will be presented within data listings. The data listings will be sorted by treatment group, country, centre number, subject number and visit/week/day.

The treatment label for all Tables, Listings and Figures will be:

Treatment Group	Treatment label for TLF
ALX-0081 10mg	ALX-0081
Placebo	Placebo
All Subjects	Total (Tables only)

## 9. APPENDICES

### Appendix I – General schedule of study assessments

	Screening	Baseline	Treatment phase			Follow-up							AE and unscheduled visit		
			Daily PE treatment phase	Day 1 after last daily PE	Post daily PE (including PE tapering)	Day 3	Day 7	1m	2m	3m	6m	12m			
Time interval	≤12h prior to first PE on study and study drug	15min-6h prior to first PE on study and study drug	see Table 3	1 day	see Table 3	±1d	±1d	±3d	±7d	±15d	±15d	±15d	as needed		
Assessment/Activity															
Treatment with study drug			Study drug i.v. bolus	X	X	X	30 day post last PE (including tapering)- stop study drug								
PK (central lab)		X		X	X	X									X
RICO (central lab)		X		X	X	X		X	X						X
ADA (central lab)		X		X	X	X				X	X	X	X	X	X
vWF (central lab)		X		X	X	X		X	X	X	X	X	X	X	X
FVIII chromogene (central lab)		X		X	X	X		X	X	X	X	X	X	X	X
Blood type (ABO and Rh) and direct antiglobulin test (DAT) (local lab)	X														
Blood chemistry (local lab)	X	X		X	X	X		X	X	X	X	X	X	X	X
Haematology (local lab)	X	X		X	X	X		X	X	X	X	X	X	X	X
Coagulation (local lab)	X	X		X	X	X		X	X	X	X	X	X	X	X
Urine pregnancy test (local lab)	X									X		X			
Urinalysis (local lab)	X														

	Screening	Baseline	Treatment phase				Follow-up							AE and unscheduled visit
			Study drug i.v. bolus	Daily PE treatment phase	Day 1 after last daily PE	Post daily PE (including PE tapering)	Day 3	Day 7	1m	2m	3m	6m	12m	
Time interval	≤12h prior to first PE on study and study drug	15min-6h prior to first PE on study and study drug		see Table 3	1 day	see Table 3	±1d	±1d	±3d	±7d	±15d	±15d	±15d	as needed
HIV1/2, HBV, HCV (local lab)	X													
Cardiac marker (TnT or TnI) (local lab)		X		X	X	X			X				X	X
BNP or NT proBNP (local lab)		X		X	X	X			X				X	X
Brain damage markers (NSE, Sβ100) (central lab)		X		X	X	X			X				X	X
ADAMTS13 & anti-ADAMTS13-antibodies (central lab)	X				X	X			X				X	X
12-lead ECG		X		X	X	X			X	X	X	X	X	X
Informed consent	X													
Inclusion/exclusion criteria	X													
Medical history and demographics	X													
Physical examination and vital signs	X	X		X	X	X	X	X	X	X	X	X	X	X
Spent plasma retrieval				X										
Modified ITP bleeding score		X		X	X	X			X					X
Clinically relevant bleeding	X	X		X	X	X			X					X
Glasgow Coma Score	X	X c		X	X	X								
Neurocognitive battery		X		X			X						X	
Recuperate nurse sheet and/or AE diary						X	X	X	X	X	X	X	X	X

	Screening	Baseline	Treatment phase				Follow-up						AE and unscheduled visit	
			Study drug i.v. bolus	Daily PE treatment phase	Day 1 after last daily PE	Post daily PE (including PE tapering)	Day 3	Day 7	1m	2m	3m	6m		12m
Time interval	≤12h prior to first PE on study and study drug	15min-6h prior to first PE on study and study drug		see Table 3	1 day	see Table 3	±1d	±1d	±3d	±7d	±15d	±15d	±15d	as needed
PE details a				X a	X a	X a								
Prior/concomitant medication recording other than PE related treatment b	X b	X b		X b	X b	X b	X b	X b	X b	X b	X b	X b	X b	X b
AE recording		X		X	X	X	X	X	X	X	X	X	X	X

a Including RBC transfusion details

b Including concomitant medication related and simultaneous to PE.

c If abnormal at screening

